8.6. Premature Discontinuation Due to Lack of Efficacy or Adverse Events

The distribution of patients who prematurely discontinue due to lack of efficacy or adverse events during the Treatment Period and Washout Period will be summarized for the safety population across all Treatment Period visits, separately at each Treatment Period visit, and for the Washout Period. Date of discontinuation during the Treatment Period will be defined as the date of last dose of study medication. For patients who complete the Treatment Period, date of discontinuation during the Washout Period will be defined as the earliest non-missing of the date of last contact or the last observed visit date.

9. Safety Analysis

All analyses of safety will be conducted using the safety population.

No formal statistical analysis will be performed on safety outcomes; inferences, if any, will be derived through clinical review and interpretation.

9.1. Adverse Events

Details regarding the definition and reporting of an AE or a serious adverse event (SAE) are provided in the study protocol. AEs will be recorded starting with the signing of the first

informed consent. All AEs will be collected through the Washout and Safety follow up visit (or Early Termination Visit). Following the Washout and Safety follow up visit (or Early Termination Visit), all unresolved AEs that were reported by the Investigator to be probably drug related should be followed by the Investigator until the events are resolved, the patient is lost to follow-up, or the AE has stabilized.

Non-serious AEs that begin during the Observation Period will be captured as medical history in the TR03 extension study; patients who never transition from the Observation Period to the Treatment Period are screening failures and did not complete the early termination or end of study CRFs. SAEs occurring during the Observation Period will be recorded as SAEs.

Also, AEs that were ongoing at the time of a patient's completion of the TR03 core study are recorded as medical history in the TR03 extension study.

A treatment-emergent AE (TEAE) will be defined as one starting or worsening on or after the first dose of study medication during the extension study. If the start date is missing, the event is assumed to be treatment emergent.

For patients who complete study treatment through the Visit 14/End of Treatment visit, Titration Period AEs are those with an onset date from first dose date of the extension study through (first dose date + 27 days). Treatment Period AEs are those with an onset date from first dose date of the extension study through (first dose date + 349 days). Washout and Safety Follow-up AEs are those with an extension study onset date of (first dose date + 350 days) through (first dose date + 363 days). For patients who are treated and who discontinue study drug use prior to the Visit 14/End of Treatment visit yet remain on-study, AEs with an onset date on or after the first dose date of the extension study will be considered Treatment Period AEs.

For the purpose of inclusion in TEAE table summaries, incomplete AE onset and end dates will be imputed as described below.

For incomplete AE onset dates:

- If the day is missing but the month and year are known:
 - If the month and year are different from the month and year of the first dose of study drug, then use the first day of the month as the imputed onset date.
 - If the month and year are the same as the month and year of the first dose of study drug, and the end date (after any imputation) is on or after the first dose of study drug, then use the date of the first dose of study drug as the imputed onset date.
 - If the month and year are the same as the month and year of the first dose of study drug, and the end date (after any imputation) is prior to the date of the first dose of study drug, then use the end date as the imputed onset date.
- If the month is missing but the year is known (day can be either missing or known):
 - If the year is different from the year of the first dose of study drug then use Jan. 1st of the reported year as the imputed onset date.

- If the year is the same as the year of the first dose of study drug and the end date (after any imputation) is on or after the first dose of study drug then use the date of the first dose of study drug as the imputed onset date.
- If the year is the same as the year of the first dose of study drug and the end date (after any imputation) is prior to the date of the first dose of study drug, then use the end date as the imputed onset date.
- If the start date is completely missing, the event is assumed to be treatment-emergent.

For incomplete AE end dates:

- If the day is missing but the month and year are known then use the last day of the month as the imputed end date.
- If the month is missing but the year is known (and the day is either missing or known) then use Dec. 31st of the year as the imputed end date.

Adverse events will be coded according to MedDRA (version to be delineated in the clinical study report).

All AE summary tables will present system organ class (SOC) and preferred term (PT), will include counts of patients, and will be based on TEAEs. SOC will be displayed in descending order of frequency overall and then alphabetically. PT will be displayed in descending order of frequency overall and then alphabetically within SOC. A patient with two or more AEs within the same level of summarization will be counted only once in that level using the most extreme incident. Percentages will be based on the number of patients in the safety population.

In all AE summary tables, TEAEs will be presented in descending order of incidence from the SOC with the highest total incidence to the SOC with the lowest total incidence. If the total incidence for any two or more SOC is equal then the SOC will be presented in alphabetical order. Within each SOC, the PTs will also be presented in descending order of total incidence among the active treatment arms with ties at the PT level being presented in alphabetical order. At each level of patient summarization, a patient is counted once if the patient reported one or more events. Percentages will be calculated out of the number of patients in the safety population.

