The total amount of time in the Observation Period cannot exceed 12 weeks. After these 12 extended screening weeks, patients not eligible for the Treatment Period are screen failed from the study. The study periods are summarized below.

Study Period	Study Weeks	Duration
Observation Period	
Patients who do not meet the criteria to start Treatment are followed in Observation Period visits (OV) for up to 12 extended screening weeks. During this time, the patient may meet criteria and become eligible to enter the Treatment Period. If the patient does not meet the criteria to enter the Treatment Period by the end of 12 extended screening weeks (OV12), participation in the study ends and the patient is screen failed
	Up to 12 Extended Screening weeks
Treatment Period	
For patients directly entering the Treatment Period as of Visit 1a, the Treatment Period begins with Study Week 1 (Visit 1a) and ends with Study Week 50.
 
For patients entering the Treatment Period after being followed in the Observation Period, the number of weeks on treatment and the end of the Treatment Period varies. (See Table 8 in the study protocol for the details of which treatment visits are to take place).
 
The End of Treatment Visit will take place after the patient completes the last week of study drug.
	Up to 50 weeks
Washout and Safety Follow-Up Period	
The Washout and Safety Follow-up Period is two (2) weeks in duration.
 
For patients directly entering the Treatment Period as of Visit 1a and completing 50 weeks of study drug treatment, the Washout and Safety Follow-up Period should take place during weeks 51 and 52.
 
For patients entering the Treatment Period after being followed in the Observation Period, the number of weeks on treatment and the end of the Treatment Period varies; Table 8 in the Study Protocol calculates the Treatment Visit assignments for any patient entering the Treatment Period from the respective Observation Period visits. The Washout and Safety Follow-up Period will take place during the two (2) weeks after the patient completes the last week of study drug.
 
The Washout and Safety Follow-up Period Visit will take place in the week following the completion of the two (2) week Washout and Safety Follow-up Period.
	2 weeks

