3.2. Premature Discontinuation of Study Drug Treatment

3.2.1. Premature Discontinuation of Study Drug Treatment Associated with Failure-to-Improve Criterion

Patients who meet failure-to-improve criterion during the conduct of the study, will stop taking study medication.

The Failure-to-Improve criteria are as follows: Beginning on Treatment Period Visit 3 (TV3), and at every subsequent Treatment visit, patients with a worst itch NRS score \geq the worst itch NRS score at Visit 1a (or at Visit 1b in the case of patients who require the OV period) will be discontinued from study drug. Patients discontinued from study drug are to undergo the End of Treatment Visit (TV14), the Washout/Safety Follow-up Period assessment in two weeks, and receive a follow-up telephone contact 30 days following end of study drug dosing for final safety assessment.

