3.2.2. Premature Discontinuation of Study Drug Treatment For Reasons Other Than Failure-to-Improve

Patients who complete Study Drug treatment through the End of Treatment Visit 14 (TV14) (even if some doses have been missed or if the patient was followed in the Observation Period before receiving study drug treatment) are considered to have completed Study Drug treatment. Patients discontinuing Study Drug treatment prior to the maximum allowable number of Treatment Weeks (based on their entry into the study at either Visit 1a or Visit 1b) will also be considered to have prematurely discontinued Study Drug treatment. Patients discontinuing Study Drug treatment prior to End of Treatment Visit 14 will be considered to have prematurely discontinued Study Drug treatment and will be asked to complete the End of Treatment Visit (TV14) regardless of where they were in the study visit schedule, the Washout and Safety Follow-up Period Visit and the Premature Discontinuation of Study Drug Telephone Contact visit. Patients removed from the study after enrollment and who have received a dose of study drug will not be replaced.

Some reasons for premature discontinuation of Study Drug treatment include:

- Intercurrent illness
- Any intolerable Adverse Event (AE) that cannot be ameliorated or safely managed with medical intervention or one that poses undue risk to the subject if Study Drug treatment were continued in the opinion of the Medical Monitor or Investigator
- Electrocardiogram (ECG) changes summarized in protocol Section 17.4
- Opioid medication is introduced in anticipation for chronic use of greater than 2 weeks
- Any medication prescribed for chronic anti-pruritic use of greater than 2 weeks
- Development of substance abuse as determined by the Investigator.

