9.1.2. Relationship of Adverse Events to Study Drug

Association or relatedness to the study medication will be graded as either “probably,” “possibly,” or “unlikely.” For the purpose of summarization, AEs will be dichotomized into “related” (probably and possibly) and “unrelated” (unlikely).

A summary of TEAEs by relationship (“related”, “unrelated”) to study drug will be presented in a table by incidence of occurrence. A patient with two or more AEs within the same level of summarization will be counted only once in that level using the most related category. TEAEs that are missing a relationship will be presented in the summary table as “related” but will be presented in the data listing with a missing relationship.

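### For patients who stop study drug early, AE collection closes before the telephone contact planned as their final safety assessment

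*SAP*

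**What the plan says.** Section 9.1 states when collection ends: "All AEs will be collected through the Washout and Safety follow up visit (or Early Termination Visit"). After that visit it provides for continued follow-up of one group of events already known: "all unresolved AEs that were reported by the Investigator to be probably drug related should be followed".

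Section 3.2.1 covers patients stopped for failure to improve. They have the End of Treatment visit, a Washout assessment two weeks later, and then "receive a follow-up telephone contact 30 days following end of study drug dosing for final safety assessment". Section 3.2.2 covers other premature discontinuations and lists, after the End of Treatment visit, "the Washout and Safety Follow-up Period Visit and the Premature Discontinuation of Study Drug Telephone Contact visit". It gives no day for that contact.

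The study-period table in Section 3.1 times the Washout visit: "The Washout and Safety Follow-up Period Visit will take place in the week following the completion of the two (2) week" washout period.

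For patients who stop drug before Visit 14 but remain on study, Section 9.1 assigns events to a period as follows: "AEs with an onset date on or after the first dose date of the extension study will be considered Treatment Period AEs". No closing date is attached. The general TEAE definition in the same section has none either.

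**The concern.** A contact described as the final safety assessment would be expected to feed the safety data. Section 9.1 closes the window for all AEs at an earlier visit, so a site that follows it literally has no instruction to record a new event disclosed at the call. A site that follows Section 3.2.1 would probably record it. If it is recorded, the SAP's period rule places it in the Treatment Period, although its onset may be weeks after the last dose.

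Safety and tolerability are the primary objective (Section 2.1). Early stopping is built into the design: the failure-to-improve rule applies from TV3 onward at every treatment visit, and Section 3.2.2 lists intolerable AEs among the reasons for stopping. Section 9.1.7 looks specifically for events suggesting withdrawal, so the time after stopping is of direct interest. Late events in these patients could be missed at some sites, or recorded and then summarised as if they arose on treatment.

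**Working it through.** The SAP gives no figure of its own for this gap. The check is a day count and a comparison of rules.

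**Inputs** (last dose = day 0)

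| Item | Day | Source |
|---|---|---|
| Washout assessment, failure-to-improve stoppers | 14 (two weeks) | Section 3.2.1 |
| Washout visit, general timing | 15 to 21 (the week after a 14-day washout) | Section 3.1 table |
| Telephone contact, failure-to-improve stoppers | 30 | Section 3.2.1 |
| Telephone contact, other early stoppers | not stated | Section 3.2.2 |
| Telephone contact, completers | none described | Sections 3.1 and 3.2 |

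Assumption: the two weeks in Section 3.2.1 run from the last dose. If the End of Treatment visit falls some days after the last dose, the Washout visit moves later and the gap shrinks.

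**Step 1: days between close of collection and the call.** Gap = day of call − day of Washout visit.

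- Earliest Washout visit: 30 − 14 = 16 days, or 16/30 = 53% of the 30 days.
- Using the Section 3.1 timing alone: 30 − 15 = 15 days, or 15/30 = 50%.
- Latest Washout visit: 30 − 21 = 9 days, or 9/30 = 30%.

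These are shares of calendar time, not of events. The same range applies to Section 3.2.2 stoppers only if their call is also at day 30, which the SAP does not say.

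**Step 2: pass one event through the rules.** Take a failure-to-improve stopper who remains on study, has the Washout visit by day 21, and first reports at the call a new event with onset on day 25.

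| Rule | Result |
|---|---|
| Collection window (9.1) | Outside: 25 > 21 |
| Final safety assessment (3.2.1) | Within the contact's remit on a plain reading |
| TEAE definition (9.1) | TEAE: onset after first dose, no upper limit |
| Period rule for early stoppers (9.1) | Treatment Period AE |

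The event is therefore not collected under one rule, yet counts as a Treatment Period AE under another.

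**Step 3: completers.** Their Treatment Period runs to first dose + 349 days and their Washout period from + 350 to + 363, that is 363 − 350 + 1 = 14 days. No later contact is described, so this conflict does not arise for them.

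**The case against.** The strongest reply is that Section 9.1 refers AE definition and reporting to the protocol, which may say what is recorded at the call. The call could also serve only to check known unresolved events, which Section 9.1 already expects to be followed past the Washout visit. Further, the absence of an upper onset date means any event that is recorded does reach the TEAE tables, and the primary endpoint concerns treatment weeks 5 to 50, to which an event weeks after the last dose is peripheral.

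Part of this stands. The protocol may settle the matter, nothing in Section 3.2.1 forbids recording a new event, and no effect on a reported rate can be shown. But Section 9.1 does not stay silent: it states a closing visit for all AEs, and that visit precedes the contact in Section 3.2.1. The open-ended period rule helps only with counting. It does not cause an event to be collected, and it gives a late event a label that does not fit.

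Three stronger readings are tempting and are not supported:

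- A reader might infer that following unresolved events rated probably related contradicts the definition of related, since "AEs will be dichotomized into “related” (probably and possibly) and “unrelated” (unlikely"). That grouping is stated to be for summarisation, whereas the follow-up sentence concerns investigator conduct and does not forbid other follow-up. The continued laboratory testing in Section 9.3 adds to it. The two rules can coexist. The lack of a separate rule for unresolved SAEs is likewise a reporting detail that the SAP leaves to the protocol.
- A reader might infer that all 30 days are lost when the Early Termination visit closes collection. The SAP does not time that visit, and Section 4.1 links it to patients leaving the study. Sections 3.2.1 and 3.2.2 instead send patients who stop drug to the End of Treatment visit, the Washout visit and the call. Nothing shows a patient for whom an early closing visit and the 30-day call both apply.
- A reader might infer that every patient has a 30-day contact. Day 30 is stated only for failure-to-improve stoppers.

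**Conclusion.** The point holds for patients who stop study drug early. Section 9.1 ends AE collection at the Washout visit, and Section 3.2.1 places the final safety assessment 9 to 16 days later. The length of any gap for Section 3.2.2 stoppers is unknown because no day is given. The range rests on the Washout visit falling 14 to 21 days after the last dose.

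The conflict has two parts: whether a new AE or SAE first reported at the call is collected, and, if it is, whether it belongs to the Treatment Period. The SAP's statements lead to different answers. It does not follow that late events will in fact be lost, since sites may record them or the protocol may require it, and the effect on any AE rate cannot be estimated from the SAP. The correction is worth making because safety is the primary objective and the contact is already planned.

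**What to change.** Reconcile Sections 3.2.1, 3.2.2 and 9.1:

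1. In Section 9.1, state that AEs and SAEs are collected through the patient's last planned safety contact, meaning the Washout visit or the telephone contact, whichever is later.
2. State the day of the telephone contact in Section 3.2.2, or refer to where the protocol gives it.
3. State that events first reported at the call enter the TEAE listings and tables as post-treatment follow-up events and not as Treatment Period AEs. An event whose onset proves to lie on treatment should keep the period of its onset. The present rule also puts an early stopper's events between the last dose and the Washout visit into the Treatment Period, so the text must say where the new category begins.
4. Check that the protocol's collection window agrees.

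The cost is wording plus a few more AE records. Early stoppers would be observed to day 30 and completers to about days 14 to 21, so the window would be 9 to 16 days longer for early stoppers. A table footnote should say so, and keeping the call events in their own category stops that difference from inflating Treatment Period incidence.

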9.1.1. Incidence of Adverse Events

An overview summary of the number and percentage of patients with any TEAE and the total number of TEAEs recorded will be presented for: patients experiencing any TEAE, any treatment-emergent SAE, any related TEAE, any TEAE by maximum intensity, and any TEAE by treatment period for the Treatment Period and Washout and Safety Follow-up Period.

The overview summary will be repeated for the Treatment Period and Washout and Safety Follow-up Period. For an AE that is reported during more than one of these periods, the earliest period of onset will be used in the incidence calculation. Additionally, the overview summary will be repeated for the Titration Period. Since the Titration Period is a subset of the Treatment Period, AEs will be reported in both periods, where applicable.

Summaries of the total number of TEAEs and the number and percentage of patients with at least one TEAE will be provided by SOC and PT.

A summary of the total number of AEs occurring during the Observation Period (captured in the TR03 extension study medical history form) and the number and percentage of patients with at least one AE during the Observation Period will be provided by body system and dictionary term. New medical history for the TR03 extension study (i.e. with an onset date on or after the signing of the informed consent for the TR03 extension study) is captured in the TR03 extension study medical history form.

All AEs will be presented in a data listing for the safety population.

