9.1.3. Severity of Adverse Events

The severity of all AEs will be graded by the investigator as Grade 1, Grade 2, Grade 3, Grade 4, or Grade 5 according to the [Common Terminology Criteria for Adverse Events \(CTCAE\) version 4.03](#).

A summary of TEAEs by severity will be presented. The severity that will be presented represents the most extreme severity captured on the eCRF page (Grade 1 through Grade 5 with Grade 5 being the most severe). A patient with two or more AEs within the same level of summarization will be counted only once in that level using the most severe incident. TEAEs that are missing severity will be presented in tables as “Severe” (i.e. Grade 3) but will be presented in the data listing with a missing severity. Percentages will be calculated out of the number of patients in the safety population.

The summary of TEAEs by severity will be repeated for the Treatment Period and Washout and Safety Follow-up Period. For an AE that is reported during more than one of these periods, the earliest period of onset will be used in the incidence calculation. Additionally, the summary will also be repeated for the Titration Period. Since the Titration Period is a subset of the Treatment Period, AEs will be reported in both periods, where applicable.

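### Titration Period AEs are defined only for patients who complete treatment to Visit 14, so early stoppers' events leave the numerator of the Titration tables but the patients stay in the denominator

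*SAP*

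**What the plan says.** SAP Section 9.1 sets the AE period windows. The Titration window is introduced with a condition on who it covers: "For patients who complete study treatment through the Visit 14/End of Treatment visit, Titration Period AEs are those with an onset date". The length of that window is then given as 28 days, counted from the first dose. The Treatment window follows directly: "Treatment Period AEs are those with an onset date from first dose date of the extension study through (first dose date + 349 days"). The Washout window then runs to first dose date + 363 days.

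A separate sentence deals with treated patients who stop drug early but stay in the study, and gives them one rule: "AEs with an onset date on or after the first dose date of the extension study will be considered Treatment Period AEs". It gives them no Titration window. Patients who stop drug and also leave the study are covered by neither sentence.

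Titration Period tables are planned in four places. Section 9.1.1 says of the overview: "Additionally, the overview summary will be repeated for the Titration Period". Sections 9.1.3 (severity), 9.1.6 (AEs of special interest) and 9.1.7 (abuse-potential AEs) plan the same repeat. All four sections also say: "Since the Titration Period is a subset of the Treatment Period, AEs will be reported in both periods, where applicable".

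On the denominator, Section 9.1.3 states: "Percentages will be calculated out of the number of patients in the safety population". The general text of Section 9.1 sets the same base for all AE summary tables. Section 4.6.2 defines that population as all enrolled patients who received a dose in the extension study.

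**The concern.** Whether an event on, say, Day 10 occurred during titration depends only on its onset date and the first dose date. It cannot depend on whether the patient is still on drug at Visit 14, which for a direct entrant comes after Week 50. Section 9.1 nevertheless makes the classification depend on later completion. A patient who stops at any time before Visit 14, in Week 2 or in Week 40, loses the Titration label for all events in the first 28 days.

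The loss need not be neutral. Section 3.4 bases titration in Weeks 1-4 on tolerance, and Section 3.2.2 lists an intolerable AE as a reason for stopping. A patient who stops for an AE during titration contributes nothing to the Titration numerator, whatever the event rates are. Completion also depends on matters unrelated to titration safety: under Section 3.2.1, a worst-itch score at or above baseline from TV3 onward ends treatment.

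At stake is the accuracy of the tables that describe tolerability in the first four weeks, in a study whose primary objective is safety and tolerability. Their numerator and denominator refer to different groups of patients.

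**Working it through.** **Window lengths.** Each window runs from first dose date to first dose date + k, so it covers k + 1 days:

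- k = 27: 28 days / 7 = 4 weeks
- k = 349: 350 days / 7 = 50 weeks
- k = 363: 364 days / 7 = 52 weeks

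These agree with 4 weeks of titration, up to 50 weeks of treatment and 2 weeks of washout in Sections 3.1 and 3.4. The windows are right; the fault is in whom the first one covers.

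**Which patients get which period (Section 9.1), for an event on Day 10:**

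- Completes through Visit 14: Titration and Treatment Period.
- Stops earlier, remains on-study: Treatment Period only.
- Stops earlier, leaves the study: no period assigned.

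All three patients are in the denominator.

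**Size.** The SAP gives no AE rates and no expected completion rate, so all inputs here are assumptions. Let c be the share completing through Visit 14, p_c the share of completers with an AE in the first 28 days, and p_s the same share among early stoppers.

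- All treated: c × p_c + (1 − c) × p_s
- As written: c × p_c
- Relative understatement: (1 − c) × p_s / [c × p_c + (1 − c) × p_s]

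If p_s = p_c, the last line reduces to 1 − c, the share who stop early. If p_s > p_c it is larger. If p_s < p_c it is smaller, but still above zero as long as any stopper had an event.

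With p_c = 60% and p_s = 80%:

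- c = 70%: shown 0.70 × 60 = 42%; all treated 42 + 0.30 × 80 = 66%
- c = 50%: shown 30%; all treated 30 + 40 = 70%
- c = 40%: shown 24%; all treated 24 + 48 = 72%

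A wider set of assumptions, with d = 1 − c as the share stopping early:

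| d | p_c | p_s | All treated | As written | Share of AE patients lost |
|---|---|---|---|---|---|
| 10% | 50% | 50% | 50% | 45% | 10% |
| 10% | 50% | 80% | 53% | 45% | 15% |
| 10% | 70% | 90% | 72% | 63% | 13% |
| 30% | 50% | 50% | 50% | 35% | 30% |
| 30% | 50% | 80% | 59% | 35% | 41% |
| 30% | 70% | 90% | 76% | 49% | 36% |
| 50% | 50% | 50% | 50% | 25% | 50% |
| 50% | 50% | 80% | 65% | 25% | 62% |
| 50% | 70% | 90% | 80% | 35% | 56% |

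Over this second set, between 10% and 62% of patients with a titration AE would be missing from the numerator.

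**The case against.** The best defence is that the early-stopper sentence was written to settle the Treatment/Washout boundary, because fixed cut-offs at + 349 and + 363 days fail for patients who stop early. On that reading it does not cancel the first 28 days. The sentence calling the Titration Period a subset of the Treatment Period, and Section 9's use of the safety population throughout, would then bring early stoppers' first-28-day events into the Titration tables. This may well be the intent. It does not repair the text: the subset sentence allows an event to be counted twice only where both definitions apply, and the Titration definition applies to completers alone. Two programmers could produce different tables from the same SAP.

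A reader might go further and infer that early safety during dose escalation disappears from the report, or that everyone with dose-limiting effects is removed. The SAP does not support that:

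- Early stoppers' events remain in the overall TEAE tables and listing (9.1.1), in the all-patient tables of days to first onset for special-interest and abuse-potential AEs (9.1.6, 9.1.7) and, where they led to stopping, in the tables of AEs leading to discontinuation (9.1.4) and discontinuations by visit (8.6).
- Escalation is governed by tolerability, not forced (3.4). Patients whose dose is reduced or held and who then complete stay in the Titration numerator.
- The primary endpoint concerns TEAEs in Weeks 5-50 (3.3.1), so the Weeks 1-4 tables do not enter it.
- Patients who stop for failure to improve need not have had more titration AEs than completers, so a higher rate in stoppers is an assumption.

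These points limit the reach of the problem. They do not make the Titration tables correct.

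**Conclusion.** The point stands, limited to the Titration Period tables. As written, Section 9.1 gives those tables a completers-only numerator over an all-treated denominator, so the incidence is understated whenever any early stopper had an event in the first 28 days. This is a stated rule that gives a wrong figure, not a missing detail.

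The direction follows from the wording alone. The size does not: it depends on the share who stop before Visit 14 and on their AE rate, neither of which the SAP gives. The one general result is that the relative understatement equals the share stopping early when the two rates are equal. The 42% against 66% comparison is an illustration, not an estimate. With no inferential analysis planned (4.3, 4.8), no test or error rate is involved.

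**What to change.** In Section 9.1:

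1. Define Titration Period AEs for all safety-population patients as TEAEs with onset from first dose date through first dose date + 27 days, whether or not the patient later completes. State that events after an earlier last dose count if they fall within these 28 days; otherwise an event on Day 12 in a patient who stopped on Day 10 would still be left open.
2. Keep the completer condition only for the Treatment/Washout boundary.
3. State that early stoppers' events in this window count in both the Titration and the Treatment Period.
4. Add a period rule for patients who stop drug and leave the study.

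The safety population stays as denominator, and the tables in Sections 9.1.1, 9.1.3, 9.1.6 and 9.1.7 then follow without further change. The cost is one revision of wording in Section 9.1 and minor programming, with no new data and no change to patient management. Reported titration AE rates will be less favourable than under the present text.
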